8.6 Statistical Methods

Primary

Safety:

Incidence of adverse experiences will be descriptively summarized. Summary statistics and plots will be generated for the change from baseline values in the vital signs, ECG parameters, and selected laboratory safety parameters for subjects, as deemed clinically appropriate. Depending on the safety parameter, the difference from baseline will either be computed on the original scale (raw change from baseline) or on the log scale and back-transformed for reporting (percent change from baseline). Summary statistics for the raw laboratory safety tests, ECGs, and/or vital signs may also be computed, as deemed clinically appropriate. Results will be summarized separately by study part.

The incidence and nature of nighttime and other episodes of potential hypoglycemia, using fingerstick glucose levels and CGM data will be summarized using descriptive statistics. Modeling techniques may be employed as needed.

Pharmacodynamics

Individual maximal GIR values (GIRmax) based on LOESS smoothed data will be analyzed in a linear mixed effects model with fixed effects for treatment (i.e. glargine, MK-5160 Dose Level 1, MK-5160 Dose Level 2, MK-5160 Dose Level 3), day (Day 1, Day 12) and treatment by day interaction, a continuous covariate for BMI, and a random effect for subject. A separate model will be used for each patient population (T1DM, T2DM).

GIRmax means and 95% confidence intervals for each treatment/day will be calculated from the model. To test the primary hypothesis, the posterior probability that the true mean GIRmax level at steady state is within 1.5 and 4.5 mg/kg/min will be calculated for each MK-5160 dose on Day 12 using a non-informative prior. If this posterior probability exceeds

70% for at least one safe and well tolerated dose of MK-5160 for each population, then the primary research hypothesis will be supported.

Between treatment GIRmax comparisons (MK-5160 versus glargine) will be performed for each dose of MK-5160 and on each day, using the model.

Additional clamp endpoints that may be analyzed in a similar fashion as above include GIR AUC endpoints over the entire clamp timeframe (0-24 hours) as well as various subfractions of interest (e.g. 0-12, 12-24 hours), though these would be based on raw data and not LOESS smoothed.

Secondary

Pharmacokinetics

NCA based geometric means and 95% confidence intervals will be provided for Cmax, AUC0-24hr, Css and CL by treatment, day and population. The geometric mean accumulation ratio (Day 12 PK / Day 1 PK) and 90% CI will be calculated for Cmax and AUC0-24hr.

Scatterplots of individual PK values (Steady state AUC0-24hr, Cmax, Css) versus BMI will be plotted for each patient population.

Individual values will be listed for each PK parameter by treatment and day and the additional following (NCA-based) descriptive statistics will be provided: N (number of subjects with non-missing data), arithmetic mean, standard deviation, arithmetic percent CV (calculated as $100 \times \text{standard deviation}/\text{arithmetic mean}$), median, minimum, maximum, geometric mean, and geometric percent CV (calculated as $100 \times \text{sqrt}(\exp(s^2) - 1)$, where s^2 is the observed variance on the natural log-scale). For Tmax, only median, minimum and maximum will be calculated.

Pharmacokinetic endpoints following administration with glargine may be summarized in a similar fashion, as appropriate.

Exploratory

Pharmacodynamics

Plasma FFA, glycerol, triglycerides, β -hydroxybutyrate, glucagon and fasting morning glucose levels, following SC administration of MK-5160 or glargine will be summarized with descriptive statistics and plotted over time. More formal treatment comparisons (MK-5160 versus glargine) may also be performed. Baseline is the Day 1 Predose value.

Pharmacokinetics/Pharmacodynamics

Exploratory PK/PD plots linking PD measures (GIR, Glucose, FFA and other secondary PD measures) to PK measures (concentration at different timepoints, Cmax, steady state AUC0-24hr) may be plotted as deemed necessary. MK-5160 PK/PD relationship will be explored using an integrated PK/PD modeling approach as necessary.

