4.2.2.2 Starting Dose for This Trial

In the diabetic patient populations to be studied in this trial, the lowest dose of MK-5160 should be an effective dose to reduce the likelihood of hyperglycemia and its associated complications. Note that all patients will be domiciled and closely monitored throughout the trial, and that T1DM patients will also be receiving prandial insulin reflective of intake and pre-prandial plasma glucose, in accordance with standard clinical practice. This will reduce the likelihood of hyperglycemia. In addition, the Investigator has discretion to administer corrective fast-acting insulin via the SC pump, either as a bolus or as an infusion.

The proposed starting dose of MK-5160 in this trial is 16.0 nmol/kg SC daily for 12 days, in both the T1DM and T2DM parts. 

[REDACTED]

The projected steady-state AUC0-24hr for a daily dose of 16 nmol/kg is 31 nM*hr. [REDACTED]

[REDACTED] Thus, the NOAEL was set at the dog exposure of 814 nM*hr, which sets a margin of 26x for this initial dose of 16 nmol/kg SC. [REDACTED]

The expected accumulation of MK-5160 after SC administration is such that the steady state AUC0-24hr of 31 nM*hr is expected to be reached ~ 7 days. [REDACTED]

The first panel of Part 1 (T1DM) will be dosed initially. Dosing for the first panel of Part 2 will commence after at least four subjects have completed dosing, and a review of available preliminary safety data and initial pharmacodynamic data is completed. The decision to initiate Part 2 and proceed in Part 1 will be made by both the Investigator and Sponsor, after review of the available data, and will be communicated via a letter to the investigator.

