Inhibition of ketogenesis is an additional important desirable effect of an ideal basal insulin, and as this is almost exclusively a hepatic process, it would be expected that MK-5160 would inhibit ketogenesis. [5,6]

ketosis, β -hydroxybutyrate will be assessed.

NEFA, glycerol, and β -hydroxybutyrate will be correlated with MK-5160 PK and glucose PD to more fully understand the complete PD profile for MK-5160.

GIR will be adjusted to maintain plasma glucose levels 100 mg/dL. After and during the dosing of MK-5160 or glargine, glucose levels will be monitored at the bedside and the GIR will be adjusted accordingly. To address the primary hypothesis around GIR, the values of interest are the individual maximal GIR (GIRmax) values at steady state, which is anticipated to fall between 1.0-2.0 mg/kg/min. As detailed below (Section 8), the GIRmax values at steady state will comprise the analysis. Within each panel, glargine will be given to two of the subjects who have been randomized along with the six subjects being given MK-5160.

In addition to the key endpoints noted above, additional exploratory endpoints will be examined to achieve a richer understanding of the actions of MK-5160 in diabetic patients. Along with the analysis of GIR noted above, data on morning fasting glucose will be collected, as will extensive data on glucose levels using CGM. These data will be closely examined during the longer fasting periods during the trial, to explore the degree to which plasma glucose levels fall during prolonged fasting while subjects are on MK-5160 or glargine. This will aid in understanding the potential risk of MK-5160 to lead to hypoglycemia. As noted, the subjects will be carefully monitored for symptomatic hypoglycemia and for glucose levels requiring intervention.

MK-5160 will be administered to T2DM patients, who generally are overweight to obese and thus have increased subcutaneous tissue that may complicate absorption and thus lead to variability in PK. It is anticipated that the T2DM subjects enrolled in this trial will cover a range of BMI, and thus PK with respect to BMI will be examined.

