8.4 Analysis Endpoints

Primary:

Safety

The primary safety endpoints in this study will include all types of adverse experiences, in addition to laboratory safety assessments, ECGs, and vital signs.

Pharmacodynamics

The primary pharmacodynamic variable in this study is the glucose infusion rate (GIR) required to maintain plasma glucose at each subjects' individual clamp target, following administration of MK-5160 or glargine. To assess the primary hypothesis, individual maximal GIR (GIRmax) values at steady state (Day 12) will be used. Prior to obtaining the maximal GIR values, data will be smoothed (LOESS) to minimize variability and the potential impact of transient outliers influencing the estimation. The default smoothing function in SAS PROC LOESS, which selects an optimal smoothing parameter based on minimizing a bias corrected AIC criterion, will be used to fit an optimal smoothing function for each subject.

Additional clamp endpoints that may be analyzed in a similar fashion as above include GIR AUC endpoints over the entire clamp timeframe (0-24 hours) as well as various subfractions of interest (e.g. 0-12, 12-24 hours and 24-end for the Day 12 clamp), though these would be based on raw data and not LOESS smoothed.

Secondary:

Pharmacokinetics

The pharmacokinetic variables of interest include Cmax, Css, Steady State AUC0-24hr, CL, Tmax and t1/2 of MK-5160 after SC administration. Similar endpoints for glargine may also be of interest, as appropriate.

Exploratory:

Pharmacodynamics

The exploratory pharmacodynamic endpoints in this study include FFA, glycerol, triglycerides, β -hydroxybutyrate, glucagon and fasting morning glucose levels, following SC administration of MK-5160 or glargine. Baseline is the Day 1 Predose value.

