8.8 Sample Size and Power Calculations

Pharmacodynamics

This is the first study of MK-5160 in a diabetic patient population, and as such no variance estimates exist other than those from a single dose study in normal healthy volunteers (P001). In order to provide an approximate estimate of power, the variability observed in P001 has been used for the power calculations presented below (Table 9).

Table 9 Probability of Supporting Primary PD Hypothesis

Target GIRmax (mg/kg/min)	True GIRmax	Probability of Supporting Hypothesis
(1.5, 4.5)	1	2%
	1.5	30%
	2	86%
	2.5	99%
	3	99%
	3.5	99%
	4	86%
	4.5	30%
	5	2%

The calculations above were based [REDACTED]
[REDACTED] and N=6 per dose, and a posterior probability threshold of 70%.

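### In its standard form, the GIRmax mixed model bases the Day 12 standard error on an average of the Day 1 and Day 12 variances, although only Day 12 decides the primary hypothesis

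*Combined protocol and SAP*

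**What the plan says.** Section 8.6 (repeated in 8.1) fits one linear mixed model per population. The fixed effects are treatment (glargine and three MK-5160 dose levels), day (1 and 12) and "treatment by day interaction, a continuous covariate for BMI, and a random effect for subject". It states no residual covariance structure, no day-specific variance and no degrees-of-freedom method.

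The error bars come from this fit: "GIRmax means and 95% confidence intervals for each treatment/day will be calculated from the model". The decision step follows directly: "the posterior probability that the true mean GIRmax level at steady state is within 1.5 and 4.5 mg/kg/min will be calculated" for each dose on Day 12 with a non-informative prior, and a value above 70% counts as support. The text does not say which variance enters that posterior.

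Two other sections restrict the primary hypothesis to the later day. Section 8.4 says that "individual maximal GIR (GIRmax) values at steady state (Day 12) will be used", and Section 4.2.3.3 says that "the GIRmax values at steady state will comprise the analysis". Day 1 is the first dose, and Section 4.2.2.2 says of the starting dose that "the steady state AUC0-24hr of 31 nM*hr is expected to be reached ~ 7 days".

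**The concern.** A random subject intercept with equal-variance residuals gives both days the same total variance. The Day 12 standard error then depends as much on the spread at first dose as on the spread at steady state. If the two spreads differ, the Day 12 interval and posterior probability are miscalibrated, even though the Day 12 mean itself is estimated properly.

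Nothing in the documents supports equal spread. Day 1 is before steady state. Section 2.1 lets the second clamp run beyond 24 hours, so the maximum may be taken over a longer window. Section 8.8 says the only variance information comes from a single-dose study in healthy volunteers.

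The standard error matters most near a limit of the target range. Section 4.2.3.3 anticipates steady-state GIRmax of 1.0-2.0 mg/kg/min, which straddles the lower limit of 1.5.

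**Working it through.** **Inputs.** Target range 1.5 to 4.5 mg/kg/min (8.3). Section 8.8 uses "N=6 per dose, and a posterior probability threshold of 70" percent. Each part has 18 MK-5160 subjects (6 per dose) and 6 on glargine (2 in each of three panels), so four arms of 6. The SD is redacted. All support figures are for one dose in one population, as in Table 9.

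**Table 9 first.** With a flat prior and normal mean, the posterior is N(x̄, SE²) with SE = SD/√6. Near the lower limit, support requires x̄ > 1.5 + 0.524·SE. Solving the 86% entry at a true mean of 2:

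SE = 0.5/(1.080 + 0.524) = 0.312, so SD = 0.312 × √6 = 0.76 (0.75-0.77 allowing for rounding).

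This SD returns 1.7%, 30.0%, 86.0%, 99.6% and 100% at true means of 1, 1.5, 2, 2.5 and 3. Table 9 gives 2%, 30%, 86%, 99% and 99%, so it is reproduced. The 30% entry does not depend on the SD.

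**What the model estimates.** For each subject let b = (y1 + y12)/√2 and w = (y12 − y1)/√2. With day variances s1² and s12² and covariance c:

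- Var(b) = (s1² + s12²)/2 + c
- Var(w) = (s1² + s12²)/2 − c

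The Day 12 arm mean is (b̄ + w̄)/√2. The random-intercept model treats b and w as independent, so it assigns this mean the variance [Var(b) + Var(w)]/(2 × 6) = [(s1² + s12²)/2]/6. The covariance cancels. The true variance is s12²/6. With r = s12/s1:

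model SE / correct SE = √[(1 + 1/r²)/2] = k

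Coverage of the nominal 95% interval is 2Φ(1.96k) − 1. Support at a true mean of 1.5 is Φ(−0.524k), and at a true mean of 2 it is Φ(0.5/0.312 − 0.524k).

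**Results.** The ratio r is an assumption; the Day 12 SD is held at 0.763.

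| r = SD12/SD1 | k | Coverage, closed form | Coverage, simulated | Support at 1.5 | Support at 2 |
|---|---|---|---|---|---|
| 0.5 | 1.58 | 99.8% | 99.5-99.7% | 20% | 78% |
| 1 | 1.00 | 95% | 95% | 30% | 86% |
| 1.5 | 0.85 | 90% | 91% | 33% | 88% |
| 2 | 0.79 | 88% | 88-89% | 34% | 88% |
| limit | 0.71 | 83% | not run | 35.5% | 89% |

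The support columns are closed form. The simulation used four arms of 6, two days, a BMI covariate, an assumed within-subject correlation of 0.5, Satterthwaite degrees of freedom and 6,000 runs per cell. A Day 12-specific variance gave coverage of about 95%, support of 29-31% at 1.5 and about 85% at 2, at every ratio simulated (0.5, 1, 1.5 and 2). In posterior terms, a nominal 70% corresponds to Φ(0.524k): 66% at r = 2 and 80% at r = 0.5.

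**Limit of the remedy.** All of the above gives every arm the same variance. Suppose instead Day 12 SDs of 0.5, 0.75 and 1.0 across the doses and 0.75 for glargine (assumed). A Day 12 variance pooled over arms is (0.25 + 0.5625 + 1.0 + 0.5625)/4 = 0.594, an SD of 0.77. The SE is then 0.77/0.5 = 1.54 times the correct value at the low dose and 0.77 times at the high dose. Simulated coverage is 99.5% and about 87%, even with day-specific variances.

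**The case against.** Four objections deserve weight.

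- **The common variance is not written down.** Section 8.6 is silent on residual covariance, and a reader might infer that the plan expressly imposes a single variance. It does not. That is the standard reading of the terms listed, and this point rests on that reading.
- **A reader might infer that Day 12 error bars are too small**, reasoning that Day 1 exposure is well below steady state and that GIR, bounded at zero, spreads less when its mean is lower. Section 4.2.2.2 gives only the time to steady state. No Day 1 AUC or accumulation ratio is visible, and no passage links exposure to the spread of GIRmax. The mechanism is plausible, but the direction cannot be established from the documents.
- **The effect on the decision is small.** In the direction that mechanism suggests, support at 1.5 rises from 30% to 33-34% for ratios of 1.5 to 2. The fall to 20% needs Day 1 to be twice as variable as Day 12, and it makes the rule stricter. Section 8.7 disclaims Type I error control, and the 95% intervals do not decide the hypothesis.
- **Day-specific variances do not repair everything.** Projected steady-state AUC runs from 31 to 124 nM*hr across doses (4.2.2.2 and 4.2.2.3), a fourfold range. If spread follows exposure, the arms differ too.

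All four stand as limits on the claim. They leave the core intact: an endpoint defined on Day 12 alone is given a standard error that, by default, is half determined by Day 1, and a method without that dependence is available at little cost.

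**Conclusion.** The point holds as a cheap improvement to the model, not as a demonstrated error in the Day 12 results. It assumes the standard random-intercept form, roughly balanced data and day SDs that differ; if they are equal, nothing changes. Over assumed ratios of 0.5 to 2, Day 12 coverage runs from about 99.6% to 88%, and support at a true mean of 1.5 from about 20% to 34%, against the planned 30%. If Day 12 is the more variable day, the gain at the boundary cannot exceed 35.5 − 30 = 5.5 points, so the intervals suffer more than the 70% rule. Table 9 is internally consistent and is not in question here.

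**What to change.** In Section 8.6, replace the random intercept with an unstructured 2x2 within-subject covariance for Day 1 and Day 12, fitted by REML with Kenward-Roger degrees of freedom. State that the Day 12 posterior uses the Day 12 variance and its degrees of freedom. Name a Day 12-only ANCOVA (treatment and BMI) as the fallback if the model does not converge. The treatment comparisons on each day remain available.

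Report Day 12 SDs by arm, and add a sensitivity analysis with arm-specific variances. Without equal variances across arms, the day-specific model does not guarantee 95% coverage. With 6 subjects per arm, the arm-specific analysis is too imprecise to be more than a sensitivity check.

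The cost is a few SAP sentences and a small code change. The Day 12 variance has about 20 degrees of freedom (24 subjects − 4 arms − 1 for BMI = 19), against about 32-37 for the pooled variance at assumed correlations of 0.3-0.5. If the day variances are in fact equal, the 95% intervals become about 2-3% wider.

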2.0 TRIAL DESIGN

2.1 Trial Design

This is a randomized, active- and placebo-controlled, parallel-group, single-site, double-blind trial of MK-5160 in subjects with type 1 and type 2 diabetes mellitus (DM).

This is a two-part trial, with three panels per part. Type 1 diabetes mellitus (Part 1) and Type 2 DM (Part 2) subjects will be given daily fixed doses of MK-5160 or glargine (active comparator) in three predefined, increasing doses in each panel. The first panel in Part 1 will be the initial panel; the second panel in Part 1 and first panel in Part 2 will be initiated after review of preliminary safety and pharmacodynamics from the initial panel. Different subjects will participate in each panel.

T2DM subjects in Part 2 may be on a single anti-hyperglycemic agent (AHA) of a permissible class (metformin, DPP4 inhibitor, sulfonylurea, or alpha-glucosidase inhibitors) **or** metformin in combination with one additional permissible AHA (a DPP4 inhibitor, sulfonylurea, or alpha-glucosidase inhibitor), at stable doses for at least 8 weeks prior to screening. Subjects may also be on insulin in addition to the above, or on insulin alone.

Subjects taking metformin and/or a DPP-4 inhibitor will continue these medications at their pre-enrollment doses throughout study participation, but subjects taking a sulfonylurea or an alpha-glucosidase inhibitor will discontinue the sulfonylurea or alpha-glucosidase inhibitor at screening, at least 7 days prior to CRU admission, and remain off until the completion of dosing.

All subjects would be brought into the site on Day -4, placed on continuous glucose monitoring (CGM), and started on an appropriate dose of fast-acting insulin, to be administered via a subcutaneous (SC) pump that will remain in place for the duration of dosing. The SC pump will be placed in all subjects during the washout period with the exception of non-insulin requiring T2DM subjects. Subjects will be domiciled for the entirety of MK-5160/glargine dosing, receiving standard meals and snacks. Prandial and (if needed) rescue insulin will be dosed throughout the trial according to standard clinical practice and at the discretion of the investigator, taking both the pre-prandial glucose level (fingerstick) and the carbohydrate content of the planned meal into account. In addition, subjects will have fingerstick glucose levels checked prior to bedtime and once overnight, and as needed per the subject and/or Investigator.

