2.2 Trial Diagram

The trial/study design is depicted in [Figure 1](#), [Figure 2](#) and [Table 1](#).

Part 1 will start first, and initiation of Part 2 will occur after review of preliminary safety and pharmacodynamic results from the first panel in Part 1. Subjects will participate in only one panel. Subjects will get injections of MK-5160/glargine and placebo matched to the alternative active treatment.

[figure not shown]

Figure 1 Overall Trial Design

The general overall plan is depicted. After admission to the CRU, subjects will discontinue their home diabetes regimen (including insulin) and be placed on continuous glucose monitoring (CGM) and a SC insulin pump to control glucose (if needed). On Day -1, this will be converted to IV infusions of insulin and dextrose to set plasma glucose for dosing and first clamp on Day 1. After 24 hours, the clamp will be discontinued and subjects will resume a normal diet on MK5160/glargine. On Days 7 and 9, subjects will be partially fasted. On Day 12, subjects will undergo a second clamp for up to 30 hours, and restart their home regimen. Subjects will continue to be domiciled and observed on the home regimen, with continued pharmacokinetic assessment.

[figure not shown]

Figure 2 Study Design

Table 1 Trial Design

	Panel A ^a	Panel B	Panel C
Part 1 (T1DM)	MK-5160 16 nmol/kg or glargin 0.4 U/kg	MK-5160 32 nmol/kg ^b or glargin 0.4 U/kg ^c	MK-5160 \leq 64 nmol/kg ^b or glargin 0.4 U/kg ^c
Part 2 (T2DM)	Panel D	Panel E	Panel F
	MK-5160 16 nmol/kg ^b or glargin 0.6 U/kg ^c	MK-5160 32 nmol/kg ^b or glargin 0.6 U/kg ^c	MK-5160 \leq 64 nmol/kg ^b or glargin 0.6 U/kg ^c

^a Within each treatment panel, 6 subjects will be randomized to receive MK-5160 and 2 subjects to receive glargin according to a computer-generated allocation schedule. In addition to MK-5160 or glargin, subjects will also receive placebo (i.e., subjects receiving MK-5160 will also receive placebo matched to glargin, and subjects receiving glargin will also receive placebo matched to MK-5160).

^b The suggested doses may be adjusted downward based on evaluation of safety, tolerability, pharmacokinetic and/or pharmacodynamic data observed in previous treatment periods.

^c The suggested glargin doses may be adjusted downward or upward, based on evaluation of pharmacodynamics data observed in previous treatment periods

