 - c. Subjects without history of myocardial infarction (MI) but who are on aspirin may be enrolled. Subjects with a history of MI or atherosclerosis are not eligible.
 - d. Other conditions, such as gastroesophageal reflux disease, obstructive sleep apnea, osteoarthritis, psoriasis, mood disorders and other chronic stable conditions may be allowed, at the discretion of the Investigator and Sponsor.
4. Have a diagnosis of T1DM as defined by standard diagnostic criteria for ≥ 12 months at time of screening.
5. Have a serum C-peptide concentration ≤ 0.7 ng/mL (0.23 nM) with a concurrent plasma glucose >90 mg/dL (5 mM).

6. Be on stable doses of basal insulin over the 2-week period prior to screening and over the 2 weeks prior to dosing. Stability is defined as within approximately $\pm 20\%$ difference in total daily insulin doses. Insulin pump users will be allowed.
7. Have a total daily insulin requirement (basal plus prandial) of ≤ 1.2 units/kg.
8. Have a HbA1c $\leq 10\%$ at the screening visit.
9. Have a Body Mass Index (BMI) ≥ 18.5 kg/m² and ≤ 32 kg/m². BMI = mass (kg)/height (m)²
10. Be a non-smoker or smoker who uses no more than 5 cigarettes or equivalent (e.g., e-cigarettes) per day over the prior 3 month period also may be enrolled (at the discretion of the investigator). The subject must agree to follow the smoking restrictions defined by the CRU.
11. Be willing to comply with the trial restrictions (see Section 5.7 for a complete summary of trial restrictions).

For Part 2 (T2DM):

1. Subjects provide written informed consent/assent for the trial. The subject may also provide consent/assent for Future Biomedical Research. However, the subject may participate in the main trial without participating in Future Biomedical Research.
2. Be male, or female of non-childbearing potential between 18 to 65 years of age at the pre-trial (screening) visit.

A female of non-childbearing potential is defined as:

- a. A female who is postmenopausal without menses for at least 1 year and has a follicle stimulating hormone (FSH) value in the postmenopausal range upon pretrial (screening) evaluation,
- b. A female who is status post hysterectomy, oophorectomy or tubal ligation.

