5. T2DM subjects are not required to have been on insulin. If on insulin, subjects should have a total daily insulin requirement of ≤ 1.2 units/kg, and have been on stable doses of basal insulin over the 2-week period prior to screening and over the 2 weeks prior to dosing. Stability is defined as within approximately $\pm 20\%$ difference in total daily insulin doses.
6. In addition to the insulin criteria in #5, meet one of the following criteria:
 - a. Be on no AHA, or on metformin monotherapy or metformin plus a DPP4 inhibitor at stable doses for at least 8 weeks prior to screening, with a screening HbA1C ≥ 7.0 and $\leq 10.0\%$.

- b. Be on either a sulfonylurea (e.g. glyburide) or an alpha-glucosidase inhibitors (e.g., acarbose) alone or in combination with metformin at stable doses for at least 8 weeks prior to screening with a screening HbA1C ≥ 7.0 and $\leq 9.0\%$. Subjects on these medications must be willing to stop the sulfonylurea or alpha-glucosidase inhibitor after screening once they qualify for study participation.
- 7. Have a BMI $\geq 18.5 \text{ kg/m}^2$ and $\leq 35.0 \text{ kg/m}^2$ BMI = mass (kg)/height (m) 2
- 8. May be on selected standard medications for T2DM, including alpha-glucosidase inhibitors (e.g., acarbose), sulfonylureas (e.g. glyburide), DPP-4 inhibitors, and metformin. Subjects on alpha-glucosidase inhibitors and/or sulfonylureas must stop these medications for at least one week prior to checking into the site and for the duration of the trial through the last dose of MK-5160/glargine. Subjects on metformin or DPP-4 inhibitors may continue on their home dose for the duration of the trial. Subjects on SGLT2 inhibitors (gliflozins), thiazolidinediones or GLP-1 agonists are excluded.
- 9. Be a nonsmoker or smoker who uses no greater than 5 cigarettes or equivalent (e.g., e-cigarettes) daily over the prior 3 month period. Subjects must agree to follow the smoking restrictions defined by the CRU.
- 10. Be willing to comply with the trial restrictions (see Section 5.7 for a complete summary of trial restrictions).

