5.4 Stratification

No stratification based on age, sex or other characteristics will be used in this trial.

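### The GIRmax model adjusts only for BMI, although insulin dose and insulin use at entry are known and could cut between-subject variance in six-subject dose panels

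*Combined protocol and SAP*

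**What the plan says.** Section 8.6, repeated in the 8.1 summary, fits a linear mixed model to GIRmax from Days 1 and 12, separately in T1DM and T2DM. Treatment has four levels: "glargine, MK-5160 Dose Level 1, MK-5160 Dose Level 2, MK-5160 Dose Level 3". The remaining terms are day, treatment by day, "a continuous covariate for BMI, and a random effect for subject". There is no panel term. The primary rule asks whether the Day 12 posterior probability that a dose mean lies between 1.5 and 4.5 mg/kg/min exceeds 70%.

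On the design, 2.1 states: "Different subjects will participate in each panel". Under Table 1 in 2.2, "Within each treatment panel, 6 subjects will be randomized to receive MK-5160 and 2 subjects to receive glargin". Section 5.2.1.2 has the previous dose level reviewed before escalation. Section 5.4 states: "No stratification based on age, sex or other characteristics will be used in this trial".

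On what is known at baseline, 5.1.2 Part 1 criterion 7 begins "Have a total daily insulin requirement (basal plus prandial" and caps it at 1.2 units/kg. Part 2 criterion 5 says "T2DM subjects are not required to have been on insulin" and applies the same cap to those who are. Section 7.1.1.5.1 records prior medication over 14 days. Section 4.2.2.1 sets the Part 2 glargine dose with insulin resistance in mind, and 4.2.2.3 anticipates resistance of about 1.5 to 2 times in T2DM.

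**The concern.** GIR at a given insulin dose depends on how sensitive the subject is to insulin. BMI is an indirect marker of that. Insulin dose per kg in T1DM, and insulin treatment in T2DM, are plausible further markers that need no new sample or visit.

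Precision matters here because each dose mean rests on six subjects and 4.2.3.3 expects steady-state GIRmax of 1.0 to 2.0 mg/kg/min, a range that straddles the lower limit of 1.5.

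The comparisons are a second matter. Subjects are randomised 6:2 within a panel, while the model pools glargine over three panels. Of the 3 × 2 = 6 glargine subjects in a population, only 2 were randomised alongside any one dose. Dose-to-dose and dose-to-pooled-glargine contrasts therefore compare largely non-concurrent groups, with BMI as the only adjustment. The random subject effect handles the Day 1 and Day 12 correlation and does nothing for differences between panels.

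**Working it through.** **Plan's own figure.** The SD behind Tables 8 and 9 is redacted, so I solved it from the 86% row. With a flat prior and known SD, support near the lower limit is Φ((μ − 1.5)/SE − z₀.₇₀).

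- SE = 0.5/(z₀.₈₆ + z₀.₇₀) = 0.5/(1.080 + 0.524) = 0.312.
- SD = 0.312 × √6 = 0.763 (0.75 to 0.77 allowing for rounding of the 86%).
- With this SD, support at true means 1, 1.5, 2, 2.5 and 3 is 1.7%, 30.0%, 86.0%, 99.6% and over 99.9%. The stated values are 2%, 30%, 86%, 99% and 99%. The upper half is symmetric.

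**Degrees of freedom.** Each model has 24 subjects. Four treatment means and BMI leave 19 between-subject df; one more covariate leaves 18.

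**Assumptions.** r is the correlation of the new covariate with GIRmax given BMI, a value the documents do not supply. The SD of 0.763 is taken as the patient SD given BMI. Only Day 12 is used. Covariates are treated as normal, which is an approximation for insulin use yes/no.

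**Precision of one dose mean, evaluated at the 24-subject covariate average.** Estimating k slopes inflates the variance on average by c = 1 + 6 × k(1/6 − 1/24)/(19 − k). This gives 1 + 0.75/18 = 1.042 for BMI alone and 1 + 1.5/17 = 1.088 with one more covariate. In units of SD²/6, the sampling variance is 1.042 before and r²/4 + (1 − r²) × 1.088 after. The r²/4 term is the sampling error of the 24-subject covariate average, which adjustment does not remove. The model's own SE² omits that term.

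Support at 2.0 is Φ((0.5 − t₀.₇₀ × model SE)/sampling SD), with t₀.₇₀ = 0.533 (19 df) or 0.534 (18 df).

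| Model | Sampling SD of dose mean | Change | Model SE | Support at 2.0 |
|---|---|---|---|---|
| BMI only | 0.318 | – | 0.318 | 85.1% |
| Added, r = 0 | 0.325 | +2% | 0.325 | 84.2% |
| Added, r = 0.3 | 0.314 | −1.4% | 0.310 | 85.7% |
| Added, r = 0.5 | 0.292 | −8% | 0.282 | 88.4% |
| Added, r = 0.6 | 0.276 | −13% | 0.260 | 90.4% |

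A simulation of the same model agrees to within about half a percentage point. The starting value is 85% and not 86% because the BMI slope and the variance are estimated here. At a true mean of exactly 1.5, support stays near 30% whatever the SE.

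**Break-even.** Setting r²/4 + (1 − r²) × 1.088 equal to 1.042 gives r ≈ 0.23.

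**Contrasts between two groups of six.** The inflation is 1 + k/(19 − k), that is 1.056 and then 1.118. The SE ratio is √((1 − r²) × 1.118/1.056): 1.03 at r = 0, then 0.98, 0.89 and 0.82 at r = 0.3, 0.5 and 0.6.

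**The case against.** - **The variance is borrowed.** Section 8.8 says the power table uses variability from a single-dose healthy-volunteer study. That SD need not contain variance due to insulin requirement or insulin treatment, so shrinking it is only illustrative. This stands, and so the sizes above are a range and not a prediction.
- **The primary rule is an absolute mean per dose.** A reader might infer that a panel with more resistant subjects biases its dose mean and makes the posterior wrong. The documents do not support that. Chance enrolment of such subjects is ordinary between-subject variance, already in the SE and the posterior, and nothing shows that enrolment drifts systematically from panel to panel. The case for the primary rule is precision alone.
- **The two glargine subjects in a panel could be of one type.** This has no bearing on the analysis, because the model pools glargine and never makes a within-panel contrast.
- **Insulin dose is not a named analysis variable.** It appears as an eligibility ceiling with a stability margin of about 20%, and within the medication record. That stands, and a derivation rule is needed.
- **The choice of covariate is a judgement.** The protocol's remarks on resistance compare populations, which the separate models already handle; applying them to individuals is inference. Metformin use or HbA1c could also be argued for. A single slope across glargine and a partial agonist cannot be tested with six per group. These points favour reporting both models, but they do not remove the possible gain.
- **This is Phase 1**, with a 70% threshold and no Type I error control (8.7). That limits the weight of the point.

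**Conclusion.** The point holds as a modest, inexpensive improvement and not as an error in the plan. BMI is the only baseline covariate, more direct markers of insulin sensitivity are already known at entry, and doses are tested in separate six-subject panels. If the added covariate has a partial correlation above about 0.23 with GIRmax, precision improves. At an assumed 0.5 the sampling SD of a dose mean falls by about 8% and the SE of a contrast by about 11%, and support at a true mean of 2.0 rises by three to four points. Little changes for doses well inside 1.5 to 4.5.

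These sizes rest on an assumed correlation and an SD solved from a redacted healthy-volunteer figure. For contrasts between doses and with pooled glargine, adjustment can reduce differences between panels but cannot replace randomisation.

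**What to change.** In 8.1 and 8.6:

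- Add baseline total daily insulin (U/kg/day) to the Part 1 model and insulin treatment at entry (yes/no) to the Part 2 model. Keep BMI.
- Define the Part 1 variable: its source in the eligibility and prior-medication record, the days averaged, and the weight used.
- Evaluate dose means and posteriors at the average covariate values of the subjects in that population, and state that the 70% rule is read from this model.
- Report the BMI-only model alongside as a sensitivity analysis.

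The cost is one degree of freedom per model, 2 to 3% in SE if the covariate is unrelated to GIRmax, and a short data definition. No visit, sample or dose changes. It should be settled before unblinded GIRmax data are seen: 8.2 asks only that later changes be listed in the study report, and a covariate added then could look data-driven.
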